	Confidential	Page 16 of 20

14.3. Monitoring:

During all phases of the study (either using standard NIV mask or Lumina mask), a staff member will be present in the patient's room.

Vital signs during NIV will be recorded in real time by the staff member.

Before, during and after NIV, and electrocardiogram (ECG) will be monitored and arterial blood\ venous gas (ABG\VBG) samples will be drawn.

A particle-measuring device (Particle Plus 8303) will be placed at a distance of 1.5 meter from the patient`s face to record the level of aerosol spread.

Following each session of NIV, the patient as well as the staff member treating the patient will be asked to complete a short questionnaire regarding the comfort and ease of use of each of the masks used. Any adverse events will be captured in real time by the staff member.

15. Data Collected:

15.1. Demographics including as age, sex, DOB, height, weight and body mass index.

15.2. Past medical history including smoking status, co-morbid conditions and medication use.

15.3. Vital signs before, during and after non-invasive ventilation such as: heart rate, respiratory rate, Tidal volume, oxygen saturation, Mode of ventilation, peak Inspiratory Pressure, Pressure Support, Ventilator type and model, Trigger sensitivity, Fio2%, PEEP, blood pressure (invasive and/or non-invasive), and temperature.

15.4. Electrocardiogram (ECG) diagrams before use (historical ECG can be also use) and monitoring during use.

Title:

Doc #: CL-003

Revision: 04

Clinical trials protocol – “Lumena”;
 Safety and usability of the LUMENA non-invasive ventilation mask

Confidential

Page 17 of 20

- 15.5. Arterial blood\ Venous blood gas analysis for O₂, CO₂, pH and HCO₃ as well as serum Lactate levels before, during and after non-invasive ventilation. A maximum of 20 ml of blood will be collected from each patient.
- 15.6. Symptoms and signs during use of non-invasive ventilation (e.g. diaphoresis, anxiety).
- 15.7. Estimation of patient preference of the mask- The question shall be phrased thusly: which mask do you prefer?
- 15.8. Estimation of staff comfort (an analog 1-5 scale as well as recording of verbal comments) – the question shall be phrased thusly: In a scale of 1-5, 1 being very uncomfortable and 5 being very comfortable, how would you rate the mask?
- 15.9. Estimation of staff use - The question shall be phrased thusly: which mask do you prefer?

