- 15.10. Estimation of patient comfort – the question will be directed to the staff member. (an analog 1-5 scale as well as recording of verbal comments). – the question shall be phrased thusly: In a scale of 1-5, 1 being very uncomfortable and 5 being very comfortable ,how would you rate the patient's feeling with the experimental mask?
- 15.11. Device related adverse events will be reported by number, type, seriousness, severity , duration and attribution . All device and treatment related adverse events will be captured, regardless of severity.

16. Risk-Benefit Assessment

This is a feasibility proof of concept study, i.e. the nature and purpose of this study is to collect data to support research and development of the Lumena mask during noninvasive ventilation. The patients will have no direct health benefit from the use of the device.

	Date 1 st Issued: 26.12.2021	
Title: Clinical trials protocol – “Lumena”; Safety and usability of the LUMENA non-invasive ventilation mask	Doc #: CL-003	Revision: 04
	Confidential	Page 18 of 20

Expected benefit for patients and staff will arise from the future creation a safer care environment, potentially minimizing the need for bulky personal protective equipment (PPE).

The Lumena mask is considered class II device in Europe. Risk assessment has been performed and no major or intolerable risks were found. All the mitigations were documented. The risk management summary in the company’s IB demonstrates that the risks associated with the tested devices are well mitigated and are as low as reasonably practicable as defined by the applicable standards.

As for the Lumena mask usage, the protocol has been designed to decrease and minimize the risk to the patients by monitoring the respiratory parameters and using it for no more than an hour.

Expected adverse events like cough or bronchospasm may arise during inhalation study. Subjects will be monitored closely for safety and reporting of adverse events during the study including follow up until complete resolution of any adverse events.

17. Confidentiality and Information Security

Each patient will be assigned a unique identifying number and that number will be used throughout all data collection and analysis processes.

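### The only listed 1-5 patient-comfort rating (15.10) is answered by staff and names the Lumena mask alone, which conflicts with 14.3 and leaves objective 3.2.3 without a standard-mask score from that item

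*Protocol*

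**What the plan says.** Objective 3.2.3 of the protocol is comparative: patient comfort and satisfaction with Lumena against commonly used oro-nasal masks. Section 14.2 makes each patient their own control across three conditions (standard mask, Lumena without suction, Lumena with suction).

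Section 14.3 describes the collection: "Following each session of NIV, the patient as well as the staff member treating the patient will be asked to complete a short questionnaire", and the subject is "regarding the comfort and ease of use of each of the masks used".

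Section 15 then lists the items, several with prescribed wording:

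- 15.7, answered by the patient: "Estimation of patient preference of the mask- The question shall be phrased thusly: which mask do you prefer".
- 15.8, staff comfort on a 1-5 scale: "In a scale of 1-5, 1 being very uncomfortable and 5 being very comfortable, how would you rate the mask".
- 15.9, staff preference between masks.
- 15.10, patient comfort on a 1-5 scale. Here "the question will be directed to the staff member", and the prescribed wording asks "how would you rate the patient's feeling with the experimental mask".

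**The concern.** Item 15.10 departs from section 14.3 in two ways. The respondent is the staff member, where 14.3 has the patient answer as well. The wording names one mask, where 14.3 covers every mask used. Because the protocol prescribes the wording of the question, this is not a detail left to a statistical analysis plan: it decides what data exist.

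If sites ask 15.10 as written, the 1-5 patient-comfort score exists for Lumena only, and only as a staff member's estimate. The patient leaves the study within one day (14.2), so a standard-mask rating not taken during the session cannot be obtained later or reconstructed by any analysis.

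**Working it through.** No arithmetic beyond counting applies, and the protocol gives no figure to reproduce. The check sets each questionnaire item in section 15 against what 14.3 and objective 3.2.3 require.

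| Item | Respondent | Subject | Mask named | 1-5 scale |
|---|---|---|---|---|
| 15.7 | patient | preference | choice between masks | no |
| 15.8 | staff | staff comfort | mask-neutral | yes |
| 15.9 | staff | preference | choice between masks | no |
| 15.10 | staff | patient comfort | Lumena only | yes |

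1. **Scales put to the patient.** There are two 1-5 scales, 15.8 and 15.10. Number answered by the patient: 0 of 2.
2. **Conditions reached by 15.10.** There are three conditions. The wording can apply to the two Lumena conditions, although it does not separate suction on from suction off and could produce one rating or two. Standard-mask scores from this item: 0.
3. **Comparison.** A within-patient comfort difference needs a score under the standard mask and a score under Lumena. Item 15.10 supplies only the second, so the difference cannot be formed from it. Item 15.8 is mask-neutral but measures staff comfort, so it cannot fill the gap.
4. **Other comparative information.** Item 15.7 gives a patient-reported choice between masks. Item 15.6 records "Symptoms and signs during use of non-invasive ventilation (e.g. diaphoresis, anxiety"). Section 14.3 adds "Any adverse events will be captured in real time by the staff member", which may include facial pain from pressure (listed in 10.2.5). These bear on comfort, but none gives a comfort level or the size of a difference.
5. **Is a proxy needed?** Inclusion criterion 8.3 requires fully conscious, cooperative patients (Glasgow Coma Scale 14-15), and 15.7 already questions the patient directly. The protocol gives no reason why the patient could not give the rating.

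**The case against.** The strongest reply is that 14.3 already commits the trial to comfort answers from the patient on every mask. On this reading 15.10 is an additional staff rating that replaces nothing, and asking staff to estimate patient comfort is a legitimate design choice. Section 15 does not claim to list every questionnaire item, parts of it are plainly illustrative, and the questionnaire is not shown. A count of listed items therefore does not prove that no patient rating is collected. Objective 3.2.3 also does not demand a 1-5 score, and 15.7 is a patient-answered comparison that speaks to satisfaction. Section 7 names no endpoint, so nothing there says that comfort will be tested as a within-subject difference.

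Much of this stands. A proxy rating is not an error in itself, the objective is not wholly without comparative data, and loss of the standard-mask score is conditional on 15.10 being followed literally. What the reply does not remove is the prescribed one-mask wording. Even as a supplementary staff rating, a question asked about one mask in a comparative crossover cannot contribute to the comparison, and it disagrees with the every-mask coverage in 14.3. A site with both passages in hand could follow either one.

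**Conclusion.** The point holds and is minor. Item 15.10 as worded produces no standard-mask score and does not carry out what 14.3 describes. The wording conflict is certain from the text. The consequence depends on the form in use: if the questionnaire follows 15.10 and has no further patient item, the 1-5 patient-comfort score is a Lumena-only proxy; if it follows 14.3, standard-mask comfort is collected and only the inconsistent wording remains.

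The effect is confined to the comfort part of one of five secondary objectives (3.2.3). The primary safety objective and the oxygenation, ventilation and aerosol objectives are not affected.

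**What to change.** Reconcile 15.10 with 14.3. Put the mask-neutral 1-5 question of 15.8 to the patient after each of the three periods, giving three ratings per patient including one under the standard mask. If the staff estimate of patient comfort is kept, ask it after every period with identical wording that refers simply to the mask, and record it as a separate staff-reported item.

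The cost is a change to form and protocol wording, plus a few short ratings at contacts that 14.3 already schedules. Where the patient questionnaire already follows 14.3, there is no added patient burden. The change does not address the lack of blinding: patient and staff will still know which mask they are rating.

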- A. 1) Standard NIV mask [30-60 minutes]; 2) Lumena mask without suction [30-60 minutes]; 3) Lumena mask with suction [30-60 minutes].
- B. 1) Standard NIV mask [30-60 minutes]; 2) Lumena mask with suction [30-60 minutes]; 3) Lumena mask without suction [30-60 minutes].
- C. 1) Lumena mask without suction [30-60 minutes]; 2) Lumena mask with suction [30-60 minutes]; 3) Standard NIV mask [30-60 minutes].
- D. 1) Lumena mask with suction [30-60 minutes]; 2) Lumena mask without suction [30-60 minutes]; 3) Standard NIV mask [30-60 minutes].

Data required for study purposes (see below) will be collected at time of enrollment from the medical record and/or from direct questioning of the study patient.

	Date 1 st Issued: 26.12.2021	
Title: Clinical trials protocol – “Lumena”; Safety and usability of the LUMENA non-invasive ventilation mask	Doc #: CL-003	Revision: 04
	Confidential	Page 15 of 20

14.2. Intervention phase:

Following randomization, each patient will be placed on BIPAP or a CPAP (per clinical need) using either the aerosol-reducing mask (Lumena) for approximately 1-2 hours, and then on the standard NIV mask used at the department for another 1-2 hours, or vice versa according to randomization scheme. In general, ventilation at each condition will be 30-60 minutes for each condition, with variation expected due to patient clinical need. Suction will be connected/disconnected from the Lumena mask according to the randomization schemes 30-60 minutes from placement of the mask. The patients will serve as their own control (cross over design).

During each of the three study phases (use of standard NIV mask, use of Lumina mask with suction and use of Lumina mask without suction), an inhalation of 5 ml 0.9% NaCl will be administered to the patient via the mask (using an in-line connector and a standard inhalation chamber) to enhance potential for environmental spread of small particles and thus enhance the ability to discriminate between the standard mask and the Lumina masks` ability to minimize aerosol spread.

Eligible patients will be enrolled into the study, perform trial activities and exit the study within a maximum of 1 day.

The study will be performed in a hospital intensive-care setting due to the nature of the device, and the required patients population.

	Date 1 st Issued: 26.12.2021	
Title: Clinical trials protocol – “Lumena”; Safety and usability of the LUMENA non-invasive ventilation mask	Doc #: CL-003	Revision: 04

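### Section 15.11 ties the detailed adverse event record to relatedness, out of line with Sections 14.3 and 16, which set no such filter

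*Protocol*

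**What the plan says.** Three places in the Protocol deal with which adverse events are recorded.

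- Section 14.3 (Monitoring) states: "During all phases of the study (either using standard NIV mask or Lumina mask), a staff member will be present". It later adds: "Any adverse events will be captured in real time by the staff member". Neither sentence refers to relatedness.
- Section 16 (Risk-Benefit Assessment) states: "Subjects will be monitored closely for safety and reporting of adverse events during the study". The same sentence extends follow-up to the resolution of any event, again without a relatedness condition.
- Section 15.11 (Data Collected) has two sentences. The first is "Device related adverse events will be reported by number, type, seriousness, severity , duration and attribution". The second is "All device and treatment related adverse events will be captured, regardless of severity".

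The primary objective (3.1) is the safety of the Lumena mask compared with standard oro-nasal masks, and Section 1 describes the study as non-blinded.

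**The concern.** Sections 14.3 and 16 are open to every event, whereas 15.11 is worded around relatedness. The two sentences of 15.11 also differ from each other: one concerns device related events, the other adds those related to treatment. No sentence says how the scopes fit together.

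This matters because 15.11 alone says which events are described by seriousness, severity, duration and attribution. A comparison of adverse events between masks needs those items on the same basis under each mask. If an event must first be judged device related, a judgement made with knowledge of the mask decides whether it enters the detailed comparison. A later analysis plan could not repair this, because it cannot use items that were not recorded at the bedside.

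**Working it through.** No arithmetic applies: the Protocol states no figure that depends on this point. The check is a comparison of the passages.

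**Step 1. Scopes side by side.**

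| Place | Activity | Events covered | Relatedness condition |
|---|---|---|---|
| 14.3 | Capture | Any, on either mask | None |
| 16 | Reporting, and follow-up to resolution | Adverse events during the study | None |
| 15.11, first sentence | Reporting with six items | Device related | Yes |
| 15.11, second sentence | Capture | Related to device or treatment | Yes |

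Capture is therefore worded in two ways (14.3 and the second sentence of 15.11), and so is reporting (16 and the first sentence of 15.11).

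**Step 2. Can all the passages be followed at once?** Yes, on a lenient reading: staff capture everything, and device related events are then described in detail. On that reading the second sentence of 15.11 is simply narrower than what is done. The six items still attach only to events judged device related, so the relatedness judgement still comes before the detailed record.

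**Step 3. What does device related mean for the comparator?** The Protocol does not settle this. Section 12 uses the term study device for Lumena. Section 10 groups effects specific to the device and effects not specific to it under one device related heading, which points to a wider sense. Section 15.10, the neighbouring item, asks staff only about the experimental mask. A reader could apply 15.11 to both masks or to Lumena alone. In the second case, events on the standard mask would have no stated descriptive items to compare with.

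**Step 4. A test case from the Protocol itself.** Section 14.2 says that in each of the three conditions "an inhalation of 5 ml 0.9% NaCl will be administered to the patient via the mask", and gives the purpose as "to enhance potential for environmental spread of small particles". Section 16 then says: "Expected adverse events like cough or bronchospasm may arise during inhalation study". Suppose bronchospasm follows the inhalation.

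- Under 14.3 it is captured, and under 16 it is reported and followed up.
- Under the second sentence of 15.11 it is captured if the inhalation counts as treatment, which 14.2 does not say.
- Under the first sentence of 15.11 it is described by the six items only if it is judged device related. Section 10 does not list it.

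The event is not lost, but its detailed description is not assured.

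**Step 5. Which safety data are outside the problem?** Items 15.3 to 15.6 (vital signs, ECG, blood gases, symptoms and signs) carry no relatedness condition and are unaffected. Item 15.6 could note a cough, but it does not list seriousness, severity or duration.

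**Step 6. Size.** The Protocol gives no event rates and no basis for how often events would be judged related under each mask. Neither the size nor the direction of a bias follows from it.

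**The case against.** The strongest reply is that there is no contradiction. Section 14.3 fixes capture for everything, 15.11 adds how one class of events is to be described, and 15.11 contains no word such as only. Listing attribution among the items even suggests that a wider set was in mind, since attribution adds little once an event is already called device related. Cough and bronchospasm are named in Section 16 and fall under its reporting and follow-up. The second sentence of 15.11 may reach them too, if effects of a study inhalation count as treatment related. Nor would rewording blind anyone: detection, severity grading and attribution would still be done with the mask known.

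Much of this stands. The passages are not aligned, but they can be reconciled, and a reader who infers that 15.11 forbids recording unrelated events goes beyond the text. It would also be tempting to count how many of the named effects 15.11 covers. The documents do not support such a count: Section 10 puts both of its lists under one device related heading, the treatment related wording widens the second sentence, and a list of possible effects is not a rule on what must be reported.

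What the reply does not remove is the filter on the detailed items. It remains under the lenient reading, and it is a stated rule rather than detail left for another document. Rewording would not make the assessment blind, but it would stop an unblinded judgement from deciding which events are described.

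**Conclusion.** The point holds as a misalignment that should be corrected. Section 15.11 is narrower than 14.3 on capture and narrower than 16 on reporting, and it is the only source of the descriptive items. If it is followed as written, the adverse event part of the primary comparison depends on a prior relatedness judgement by people who know the mask, with an unclear meaning of device for the standard mask and uncertain detail for events the Protocol itself expects from the inhalation.

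The consequence is conditional on 15.11 being applied literally, and no passage says that it overrides 14.3 or 16. The primary objective is weakened in one component, not defeated, because the measurements in 15.3 to 15.6 do not pass through the filter. A reader might infer that the comparison is tilted in favour of Lumena. The documents do not support that, since they give nothing from which a direction or size could be derived.

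**What to change.** Reword 15.11 so that all adverse events in all three conditions (standard mask, Lumena with suction, Lumena without suction) are captured and reported with the six items it already names, and by the mask and suction condition in use at onset. State that relatedness is recorded as an attribute of each event and is not a condition for recording or describing it. This brings 15.11 into line with 14.3 and 16, which need no change.

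The cost is one reworded item, a few extra fields for events judged unrelated, and a slightly longer safety table. Capture of those events is already provided for in 14.3, so the added work lies in describing them.
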